6.1.1 Triapine

Patients will be instructed to take triapine PO at the assigned dose level. Triapine will be administered on Days 1-14 of every 8 week cycle to overlap with the four administrations of Lutetium Lu 177 Dotataate. On Day 1 of each cycle, patients will ingest one dose of triapine within 90 minutes after Lutetium Lu 177 Dotataate treatment. Triapine will be discontinued after the last cycle of Lutetium Lu 177 Dotataate administration since triapine does not have anti-tumor activity by itself.

Patients will be asked to fast (except for water) for 2 hours prior to dosing and for 1 hour after ingesting the oral dose. Capsules should not be opened.

Missed doses for any reason, including vomiting, can be taken up to 6 hours after the scheduled dose. If it has been more than 6 hours since the missed dose, this dose should be skipped.

6.1.2 Lutetium Lu 177 Dotataate:

Lutetium Lu 177 dotataate and related supportive care drugs will be administered per participating institution standard operating procedure per FDA approved label indication, dose and route of administration. Please refer to section 8.2.1 for details regarding Lutetium Lu 177 Dotataate route of administration.

Somatostatin Analogs: If patients were on somatostatin analog long acting release (SSA-LAR) depot injections prior to enrollment in the trial, they will continue to be on SSA LAR during the trial. Patient will need to discontinue long-acting somatostatin analogs for at least 4 weeks prior to initiating Lutetium Lu 177 dotataate unless long-acting somatostatin analog is required for control of patients carcinoid syndrome. Patient can receive either long acting octreotide 30 mg every 4 weeks as deep intramuscular depot injection or lanreotide 120 mg every 4 weeks as deep subcutaneous injection, per FDA guidelines. Injections are administered in the superior external quadrant of the buttock.

Patients who need rescue short-acting octreotide to control their functional neuroendocrine symptoms per recommendations of their treating physician.

Antiemetic: Administer antiemetics 30 minutes before the recommended amino acid solution.

Amino Acid Solution: Initiate an IV amino acid solution containing L-lysine and L-arginine (Table 1) 30 minutes before administering Lutetium Lu 177 Dotataate. Use a three-way valve to administer amino acids using the same venous access as Lutetium Lu 177 Dotataate or administer amino acids through a separate venous access in the patient's other arm. Continue the infusion during, and for at least 3 hours after Lutetium Lu 177 Dotataate infusion. Do not decrease the dose of the amino acid solution if the dose of Lutetium Lu 177 Dotataate is reduced.

Table 1. Amino Acid Solution	
Item	Specification
Lysine HCl content	Between 18 g and 24 g

Arginine HCl content	Between 18 g and 24 g
Volume	1.5 L to 2.2 L
Osmolarity	< 1050 mOsmol

6.2 Definition of Dose-Limiting Toxicity

DLT will be defined by Grade 3 or greater hematological or non-hematological toxicity per CTCAE version 5.0 that is **possibly, probably or likely** related to study treatment. The following will not be considered DLTs unless determined to be clinically significant and related to study treatments by the treating physician:

- Grade 1-4 lymphopenia
- Grade 3 nausea, vomiting or diarrhea lasting <72 hours and controlled by optimal antiemetic/anti diarrheal therapy;

DLT will be assessed at the end of Cycle 1. Patients need to have at least one dose of Lutetium Lu 177 Dotatate and at least 80% of the dose cohort-specific triapine during Cycle 1 to be evaluable for adverse effects and DLT criteria for dose escalation/de-escalation decisions.

Management and dose modifications associated with the above adverse events are outlined in Section 7.

Dose escalation will proceed within each cohort according to the BOIN design described in Section 9.1. Dose-limiting toxicity (DLT) is defined above.

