9. STATISTICAL CONSIDERATIONS

9.1 Study Design/Endpoints

This study is a multicenter phase 1 trial of triapine and Lutetium Lu 177 Dotatace in combination for well-differentiated somatostatin receptor-positive GEP-NETs after the failure of at least one line of prior systemic cancer treatment. An expansion cohort with 14 additional patients will be enrolled at the RP2D to further assess safety, obtain initial estimates of clinical response outcomes, and perform exploratory comparisons of biomarkers.

The primary objective of the **phase 1 trial** is to determine the MTD and identify the RP2D of triapine in combination with Lutetium Lu 177 Dotatace. The Bayesian optimal interval design (BOIN) (Yuan *et al.*, 2016) will be employed to guide dose escalation. DLT is defined in Section 6.2 and will be assessed after the first cycle (8 weeks post treatment). Patients will be enrolled in cohorts of 3 beginning at dose level 1. A target DLT rate of 25% will be assumed with dose escalation, λ_e , and de-escalation boundaries, λ_d , set at 0.197 and 0.298, respectively. Based on the BOIN design, dose escalation will proceed as shown in the table below until a total of 15 patients have been enrolled in the dose escalation part of this phase 1 trial. MTD and RP2D will be estimated using isotonic regression based on toxicity data from all patients.

Dose escalation and de-escalation boundaries Table

Number of patients treated at the current dose:	1	2	3	4	5	6	7	8	9	10	11	12	13	14	15
Escalate if DLTs \leq	0	0	0	0	0	1	1	1	1	1	2	2	2	2	2
De-escalate if DLTs \geq	1	1	1	2	2	2	3	3	3	3	4	4	4	5	5

An expansion cohort with 14 additional patients will be enrolled at the RP2D to further assess safety, obtain initial estimates of clinical response outcomes, and perform exploratory comparisons of biomarkers. Assuming that the minimum number of patients enrolled at the RP2D is equal to 17, the proposed sample size from the phase 1 portion and expansion cohort will produce a two-sided 95% exact confidence interval with a width equal to 0.44, when the DLT rate is 0.25.

Interim Analysis for Phase 1 (Dose escalation)

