For the Phase 1 portion of this study, all decisions regarding dose escalation/expansion/de-escalation require sign-off by the Protocol Principal Investigator through the CTMS/IWRS. In addition, for the Phase 1 portion, the Protocol Principal Investigator will have at least bi-monthly, or more frequently, conference calls with the Study Investigators and the CTEP Medical Officer(s) to review accrual, progress, adverse events, and unanticipated problems. DLT will be assessed as defined in Section 6.2 using CTCAE version 5.0 which will be assessed after the first cycle for each patient enrolled in the trial. The dose escalation and cohort sizes are specified in the table above. Automated triggers developed by the Biostatistics and Bioinformatics Shared Resource at Markey Cancer Center (MCC) will be run after each patient is enrolled in order to perform real-time evaluation of DLT to make recommendations to the study team to implement the dose

escalation rule defined in the Table above. The Protocol Principal Investigator will make dose escalation decisions based on evaluation of all patient data, including type of DLT and non-DLT events. The appropriate dose level available for patient enrollment is made available in the OPEN and IWRS system described in Section 4.3.

Expansion Cohort Safety Assessment

For the expansion cohort, patients will continue to be monitored for occurrence of DLT. If 2 of the first 5 patients or if ≥ 2 of 6 patients experience DLT, the PI will discuss with all study investigators and with CTEP whether further addition of patients is needed to re-assess the RP2D; isotonic regression will also be utilized to estimate the DLT rate. Monitoring of all safety and toxicity data is done by the PI and the Corresponding Organization on a real-time basis as data are entered into Medidata Rave using the Web Reporting Module. All participating sites are expected to notify the PI when a DLT has occurred.

Analysis of Safety Data

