The MTD will be estimated using isotonic regression based on observed DLT from all patients enrolled in the phase 1 portion and expansion cohort. All patients who received study drugs will be included in the safety analysis. DLTs based on Section 6.2 will be summarized descriptively at each dose level. Adverse events will be summarized based on CTCAE version 5.0. The maximum grade of toxicity for each adverse event category of interest will be recorded for each patient and the summary results will be tabulated by category and grade. We will describe all serious (\geq grade 3) toxicity events on a patient-by-patient basis. Frequency and incidence tables of toxicity and adverse events will be generated in the overall patient group and by dose level depending on patient enrollment.

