12.1.1 Definitions

Evaluable for toxicity. All patients will be evaluable for toxicity from the time of their first treatment with study treatment.

Evaluable for objective response. Only those patients who have measurable disease present at baseline, have received at least three cycle of therapy, and have had their disease re-evaluated post-baseline will be considered evaluable for response. These patients will have their response classified according to the definitions stated below. Patients who exhibit objective disease progression prior to the end of Cycle 1 will also be considered evaluable.

Evaluable Non-Target Disease Response. Patients who have lesions present at baseline that are evaluable but do not meet the definitions of measurable disease, have received at least one cycle of therapy, and have had their disease re-evaluated will be considered evaluable for non-target disease. The response assessment is based on the presence, absence, or unequivocal progression of the lesions.

24-Month Progression-Free Survival: 24-month PFS is defined as the percentage of patients alive with no evidence of radiological progression per RECIST 1.1 at 24 months from the time of enrollment.

Overall survival: OS is defined as the time from date of enrollment to the date of death due to any cause.

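### Section 6.2's 80% triapine rule has no exception for a DLT that causes the shortfall, and the plan does not say whether its DLT estimates apply that rule

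*Combined protocol and SAP*

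**What the plan says.** Section 6.2 makes evaluability conditional on at least one Lu 177 dotatate dose and "at least 80% of the dose cohort-specific triapine during Cycle 1 to be evaluable for adverse effects and DLT criteria". The sentence ends by tying this to "DLT criteria for dose escalation/de-escalation decisions". No section says what happens when a DLT itself causes the shortfall, and there is no rule for replacing non-evaluable patients.

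Other sections describe wider sets:
- 9.1, design: "MTD and RP2D will be estimated using isotonic regression based on toxicity data from all patients".
- 9.1, interim analysis: DLT is assessed for each enrolled patient, and the investigator decides "based on evaluation of all patient data, including type of DLT and non-DLT events".
- 9.1, safety analysis: the MTD estimate uses "observed DLT from all patients enrolled in the phase 1 portion and expansion cohort", and "DLTs based on Section 6.2 will be summarized descriptively at each dose level".
- 12.1.1: "All patients will be evaluable for toxicity from the time of their first treatment with study treatment".
- 6.3: the RP2D rests on 15 treated patients at 100, 150 and 200 mg.
- 9.4.1: 15 patients were enrolled in escalation. The DLT estimate at dose level 2 is 0.18, with a probability of 0.25 that the rate exceeds 0.25. It refers to evaluable patients but gives no numerator or denominator.

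**The concern.** A minimum-exposure rule is meant to remove patients who had too little drug to show toxicity. It should not remove patients who had little drug because they showed toxicity. As written, the 6.2 rule does not separate the two, so the exclusion can depend on the primary endpoint.

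Section 7.2 supplies the mechanism. It holds triapine for refractory Grade 3 nausea, vomiting or diarrhea and for Grade 3 events in its general non-hematologic table, and ends protocol therapy for Grade 4 events. Many of these are DLTs under 6.2. Section 7.2.1 adds a direct example: an arterial pO2 below 80 counts as a DLT with no exposure condition, yet 6.2 could make that patient non-evaluable.

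At stake are the DLT figures that support the RP2D: the dose level 2 estimate in 9.4.1 and the final isotonic regression.

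**Working it through.** **1. The plan's own boundaries.** Inputs from 9.1: target rate 0.25. With the usual BOIN multipliers (0.6 and 1.4, assumed; the documents do not state them), the alternatives are 0.15 and 0.35.
- Escalation boundary: ln(0.85/0.75) / ln[(0.25 × 0.85)/(0.15 × 0.75)] = 0.1968 (plan: 0.197).
- De-escalation boundary: ln(0.75/0.65) / ln[(0.35 × 0.75)/(0.25 × 0.65)] = 0.2984 (plan: 0.298).

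Rounding n times the first down and n times the second up reproduces every cell of the 15-column table, so the table can be used as printed.

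**2. The threshold.** Triapine is planned once daily for 14 days. 0.80 × 14 = 11.2, so 12/14 (85.7%) passes and 11/14 (78.6%) fails. Section 6.1.1 skips a dose more than 6 hours late and Appendix D allows none after Day 14, so lost doses stay lost.

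If 80% is counted in mg, the threshold is stricter after a dose reduction, which 7.2 allows after Grade 3 gastrointestinal events. Example at 150 mg: 8 full doses, 2 missed, then 4 at 100 mg gives (8 × 150 + 4 × 100)/(14 × 150) = 1600/2100 = 76%. That patient fails in mg but passes in doses (12/14). Section 6.2 does not say which applies.

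**3. Which DLTs are exposed.**
- Grade 3 nausea, vomiting or diarrhea escapes DLT status in 6.2 only if it is controlled and lasts under 72 hours (clinically significant related events aside). Triapine held for 72 hours costs three daily doses: 11/14, not evaluable.
- Serial methemoglobin sampling is scheduled for Day 9 in the escalation cohort (5.1 and the Study Calendar). A patient who stops triapine that day has at most 9/14 = 64%.
- Not exposed: Grade 3 neutropenia and thrombocytopenia, for which 7.2 makes no triapine change, and events after the twelfth full dose.

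**4. Effect on the escalation rule.** 9.1 states: "Patients will be enrolled in cohorts of 3 beginning at dose level 1". Compare x DLTs in n with (x − 1) in (n − 1), reading the 9.1 table:

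| Counted | Action | One DLT patient dropped | Action |
|---|---|---|---|
| 1/3 | de-escalate | 0/2 | escalate |
| 2/3 | de-escalate | 1/2 | de-escalate |
| 1/6 | escalate | 0/5 | escalate |
| 2/6 | de-escalate | 1/5 | stay |
| 3/6 | de-escalate | 2/5 | de-escalate |
| 1/9 | escalate | 0/8 | escalate |
| 2/9 | stay | 1/8 | escalate |
| 3/9 | de-escalate | 2/8 | stay |

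The action changes at 1/3, 2/6, 2/9 and 3/9. Each change is in the less cautious direction.

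**5. Effect on an estimate.** The documents give no counts, so these are assumed. Restoring one dropped DLT moves a raw rate from 1/5 to 2/6 (0.20 to 0.33) or from 1/8 to 2/9 (0.13 to 0.22). At the 17 patients that 9.1 takes as the minimum at the RP2D, with 4 DLTs (nearest to 0.25 × 17 = 4.25), dropping one gives 3/16 = 0.188 instead of 4/17 = 0.235.

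**The case against.** The best defence is scope. The filter in 6.2 is worded for escalation and de-escalation decisions, which are over: the 15 patients are enrolled, and 2.5.2.1 says accrual has closed. Estimation falls under 9.1, which names all patients. Because 9.4.1 reports 15 enrolled and 6.3 reports 15 treated, those two sets coincide for escalation. The sentence that summarises DLTs by reference to 6.2 reads most naturally as pointing to the definition, not to the filter. The investigator could weigh all data, and the expansion monitoring rule states no exposure condition.

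Most of this stands. The sets for decisions and for estimation can differ without contradiction, and the literal clash with 12.1.1 is confined to the part of the 6.2 sentence that extends non-evaluability to adverse effects. What does not fall away is 9.4.1: it speaks of evaluable patients without counts, and 6.3 gives no DLT denominator per level. Discretion over a decision also does not define the set for a regression.

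A second objection is that rewriting an evaluability rule after the data are in is undesirable. That is fair, but this change can only add DLTs to the filtered set and alters no dose assignment.

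A reader might go further and infer that a DLT was dropped, or that the RP2D was chosen on a biased count. The documents do not support this: no excluded patient is reported, and the text in 6.3 points, if anything, the other way.

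**Conclusion.** The rule is wrong as written, because it can remove a true DLT from the count, and one removal changes the BOIN action in four of the eight situations tabulated. Those results rest only on the printed boundary table and on taking 6.2 literally. They describe what the rule permits, not what happened.

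The live issue is narrower. It is not stated whether the 0.18 estimate at dose level 2 applied the 6.2 filter, or whether the final regression means every enrolled patient or those meeting 6.2. With samples this small one patient matters: about 0.05 on the raw rate at n = 17 under the assumed 4 DLTs, and about 0.10 to 0.13 at n = 6 to 9 under the assumed counts. No general bias figure can be given, because the documents do not show how many patients, with or without a DLT, fell below 80%. It should be fixed before the final DLT analysis is reported.

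**What to change.** - In 6.2 and 9.1, state that any treated patient with a Cycle 1 DLT is DLT-evaluable whatever the triapine exposure, and that the 80% requirement applies only to patients without a DLT.
- State whether 80% is counted in doses or in mg.
- Reconcile the adverse-effects wording in 6.2 with 12.1.1, and the filter with the pO2 event in 7.2.1.
- Use this set for the final isotonic regression. It is slightly conservative, since a low-exposure patient enters only with a DLT, so give an all-treated estimate alongside.
- Report treated, evaluable and DLT counts per dose level, with the reason for each exclusion, and note that the rule was clarified after escalation closed.
- Re-run the dose level 2 estimate in 9.4.1 only if a DLT patient was excluded; otherwise state that none was.

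The cost is a few sentences and one count table from Cycle 1 data already collected. No patients, visits or dosing decisions are affected.

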6.3 Triapine Administration: Dose Expansion Cohort

This study's dose escalation cohort enrolled 15 patients in order to identify the recommended Phase 2 Dose (RP2D) of Triapine. The Recommended Phase II Dose (RP2D) is based on data available from 15 patients who were treated with varying doses of Triapine (100mg, 150mg and 200mg) using BOIN dose escalation design.

6.3.1 Triapine RP2D

After completion of dose escalation on 15 patients, **Dose Level 2 was selected as the RP2D** for the dose expansion cohort. Thus, all patients enrolled in the dose expansion cohort will be administered **Triapine 150mg** orally once a day on Days 1-14 of each Lu-177 dotatate cycle.

An additional 14 patients will be treated at the RP2D dose (i.e., enrolled in the dose expansion cohort). For the expansion cohort, patients will continue to be monitored for occurrence of DLT. If 2 of the first 5 patients or if ≥ 2 of 6 patients experience DLT, the Principal Investigator will discuss with all study investigators and with CTEP whether further addition of patients is needed to re-assess the RP2D. Monitoring of all safety and toxicity data is done by the Principal Investigator and the Corresponding Organization on a real-time basis as data are entered into Medidata Rave using the Web Reporting Module. All participating sites are expected to notify the Principal Investigator when a DLT has occurred.

6.3.2 Dose Expansion Treatment Regimen

Regimen Description: Dose Expansion Cohort					
Agent	Premedications; Precautions	Dose	Route	Schedule	Cycle Length
Triapine	Fast (except for water) for 2 hours prior to dosing and for 1 hour after ingesting the oral dose	RP2D is 150mg once daily (dose expansion cohort)	Oral;	Days 1-14 of each cycle; on Day 1, within 90 minutes after Lutetium Lu 177 Dotataate treatment.	8 weeks (56 days)
Lutetium Lu 177 Dotataate	Administer antiemetics 30 minutes before the recommended amino acid solution. Administer amino acid solution IV 30 minutes before Lutetium Lu 177 Dotataate.	200 mCi	IV; See 8.2.1	Day 1 of each cycle	

The patient will be requested to maintain a medication diary of each dose of triapine (Appendix D). The medication diary will be returned to clinic staff at the end of each course.

6.4 General Concomitant Medication and Supportive Care Guidelines

There are no known drug interactions with triapine. The non-radioactive form of lutetium is not an inhibitor or inducer of cytochrome P450 (CYP) 1A2, 2B6, 2C9, 2C19 or 2D6 *in vitro*. It is not an inhibitor of P-glycoprotein, BCRP, OAT1, OAT3, OCT2, OATP1B1, OATP1B3, or OCT1 *in vitro*. Because there is a potential for interaction of triapine with other concomitantly administered drugs, the case report form must capture the concurrent use of all other drugs, over-the-counter medications, or alternative therapies. The Principal Investigator should be alerted if the patient is taking any agent known to affect or with the potential for drug interactions. The study team should check a frequently-updated medical reference for a list of drugs to avoid or minimize use of. Appendix C (Patient Clinical Trial Wallet Card) should be provided to patients if available.

Risk from Radiation Exposure: Minimize radiation exposure during and after treatment with Lutetium Lu 177 Dotataate consistent with institutional good radiation safety practices and patient management procedures.

Myelosuppression: Monitor blood cell counts. Withhold, reduce dose, or permanently discontinue based on severity. Please refer to section 7 for specific guidance regarding dose modification.

Renal Toxicity: Advise patients to urinate frequently during and after administration of Lutetium Lu 177 Dotataate. Monitor serum creatinine and calculated creatinine clearance. Withhold, reduce dose, or permanently discontinue based on severity. Please refer to section 7 for specific guidance regarding dose modification.

Hepatotoxicity: Monitor transaminases, bilirubin, and albumin. Withhold, reduce dose, or permanently discontinue based on severity.

Neuroendocrine Hormonal Crisis: Monitor for flushing, diarrhea, hypotension, bronchoconstriction, or other signs and symptoms.

6.5 Duration of Therapy

In the absence of treatment delays due to adverse event(s), treatment may continue for 4 cycles or until one of the following criteria applies:

- Disease progression (patient will however be monitored for OS)
- Intercurrent illness which would, in the judgment of the investigator, a) affect assessments of clinical status to a significant degree, b) require discontinuation of drug, or c) both a and b
- Unacceptable adverse event(s)
- Delay in treatment of more than 6 weeks.
- Patient decides to withdraw from the study
- General or specific changes in the patient's condition render the patient unacceptable for further treatment in the judgment of the investigator
- Clinical progression
- Patient non-compliance
- Pregnancy
 - All women of child-bearing potential should be instructed to contact the investigator immediately if they suspect they might be pregnant (e.g., missed or late menstrual period) at any time during study participation.
 - The investigator must immediately notify CTEP in the event of a confirmed pregnancy in a patient participating in the study.
- Termination of the study by sponsor

- The drug manufacturer can no longer provide the study agent

The reason(s) for protocol therapy discontinuation, the reason(s) for study removal, and the corresponding dates must be documented in the Case Report Form (CRF).

In April-May 2022 there was a global shortage of Lutetium 177 dotatate. Study enrollment and treatment was held per NCI CTEP's recommendation. The study was not affected as all patients had received cycle 1 of treatment had cleared DLT window. Delay in treatment due to global shortage will not trigger protocol deviation and treatment will resume when drug supply is restored. Patient will then get back on treatment schedule per protocol.

